**Table 4. CTCAE Guidelines for Evaluation of AE Severity**

	Clinical Description of Severity
Grade 1	Mild; asymptomatic or mild symptoms; clinical or diagnostic observations only; intervention not indicated
Grade 2	Moderate; minimal, local or noninvasive intervention indicated; limiting age-appropriate instrumental activities of daily living (e.g., preparing meals, shopping for groceries or clothes, using the telephone, managing money, etc.)
Grade 3	Severe or medically significant but not immediately life-threatening; hospitalization or prolongation of hospitalization indicated; disabling; limiting self-care activities of daily living (e.g., bathing, dressing and undressing, feeding self, using the toilet, taking medications, and not bedridden)
Grade 4	Life-threatening consequences; urgent intervention indicated
Grade 5	Death related to AE

Severity and seriousness are not equivalent: an AE may be severe in intensity, but would be considered serious only if it meets the criteria for an SAE (described in [Section 6.5.4](#)). If an AE is deemed serious, the CTCAE severity grade reported must be consistent with this assessment.

*6.5.4. Serious Adverse Events*

Study center personnel must alert the sponsor or its designee of any serious adverse event (SAE) within 24 hours following investigator knowledge of the event via a sponsor-approved method. Alerts issued via telephone must be immediately followed with official notification on study-specific SAE forms. An SAE is any AE from this study that results in one of the following outcomes:

- Death
- Initial or prolonged inpatient hospitalization
- A life-threatening experience (that is, immediate risk of dying)
- Persistent or significant disability/incapacity
- Congenital anomaly/birth defect
- Considered significant by the investigator for any other reason.

Important medical events that may not result in death, be life-threatening, or require hospitalization may be considered serious adverse drug events when, based on appropriate medical judgment, they may jeopardize the patient and may require medical or surgical intervention to prevent one of the outcomes listed in this definition. Preplanned surgeries will

not be reported as SAEs, however if an AE occurs during hospitalization for preplanned surgery that meets the above criteria, it will be reported as an SAE. SAEs due to progressive disease (including death) should not be reported as SAEs unless the investigator also deems there is a possible contribution of the IMP.

All SAEs occurring from the time the patient signs the ICD until the 30-day Follow-up visit must be reported to the sponsor or its designee regardless of relatedness to IMP or protocol procedures. Thereafter, SAEs will be reported only if the investigator feels the events were related to the IMP or a protocol procedure. Any SAEs after ICD signature and prior to administration of IMP will be reported if the investigator feels the events were related to a protocol procedure.

Appendix 1 outlines specific safety assessments for the 30-day Follow-up visit. All drug-related AE and SAEs will be followed until the events resolve, the events are no longer considered to be drug-related, the patient dies or is lost to follow-up, or until a new treatment is initiated for the patient. Frequency of follow-up evaluation is left to the discretion of the investigator.

The medical representative of the sponsor will monitor safety data throughout the course of the study. The sponsor and/or its designee will review SAEs within appropriate timeframes to meet reporting obligations imposed by regulatory authorities. All serious and unexpected AEs for this study will be reported to regulatory authorities in accordance with local laws, directives and regulations.

#### *6.5.5. Safety Assessment Committee*

A SAC will be involved in safety oversight and decisions of dose escalation during the course of the study. Members of the SAC will include the Principal Investigator or designee from each actively enrolling study center, the medical representative(s) of the sponsor, and other representatives, as necessary. A SAC chair will be chosen. The SAC will meet by teleconference to cumulatively review the relevant data, as available. Minutes will be taken at each meeting, and all decisions made during teleconferences will be documented in writing. The sponsor or designee is responsible for notifying all study centers of any decisions made during SAC meetings.

The SAC will meet at least quarterly. In addition, the SAC will meet before opening each new MAD cohort for enrollment in Phase I.

Further information on the roles and responsibilities of the SAC can be found in the SAC Charter.

### **6.6. Product Complaint Handling**

The sponsor collects product complaints on IMPs used in clinical trials in order to ensure the safety of study participants, to monitor quality, and to facilitate process and product improvements.

Product complaints related to concomitant drugs are reported directly to the manufacturers of those drugs in accordance with the package insert.

Patients will be instructed to contact the investigator as soon as possible if they have a product complaint or problem with the IMP so that the situation can be assessed.

The investigator or his/her designee is responsible for handling the following aspects of the product complaint process in accordance with the instructions provided for this study:

- Recording a complete description of the product complaint reported and any associated AEs using the study-specific product complaint form provided for this purpose, and
- Faxing the completed product complaint form within 24 hours to the sponsor or its designee.

The investigator, when asked to return the product for investigation, will return a copy of the product complaint form with the product.

## **6.7. Efficacy Evaluations**

### *6.7.1. Radiographic Tumor Assessment*

Tumor response will be assessed by a radiologist following the RECIST guidelines v. 1.1 (Appendix 10). The schedule of tumor assessments will be maintained independent of any treatment schedule delays or changes. For any patient who discontinues the study for reasons other than radiographic progression (e.g., symptomatic progression, unacceptable toxicity), a tumor assessment will be performed at the Discontinuation visit only if  $\geq 4$  weeks has elapsed since the last tumor assessment. An unscheduled tumor assessment will be obtained in such patients if a Discontinuation visit will not be conducted. Patients who discontinue the study for reasons other than radiographic progression will be followed according to standard of care following discontinuation.

### *6.7.2. Overall Survival*

Overall survival (OS) will be monitored from the time of patient enrollment until the patient is lost to follow-up, deceased, the study is considered complete, or a maximum of 1 year is reached. The patient's medical record will be consulted approximately every 3 months to assess survival.

## **7. DATA MANAGEMENT METHODS**

### **7.1. Data Quality Assurance**

To confirm study compliance with the protocol, ICH GCP, and applicable regulatory requirements, the study may be audited, inspected, and/or monitored. The investigator will permit access to study-related documentation and study facilities for regulatory authorities, monitors, auditors, and members of the IEC/IRB for this purpose, provided patient confidentiality is maintained.

To ensure accurate, complete, and reliable data, the sponsor or its representatives will do the following:

- Provide instructional material to the study centers, as appropriate.
- Sponsor a start-up training session for the investigators and study coordinators on the protocol, data entry procedures, and study procedures.
- Make periodic visits to the study center(s).
- Be available for consultation and in contact with the study center(s) by mail, telephone, email, and/or fax.
- Review study data, documents and/or procedures for legibility, compliance, completeness, accuracy, consistency, and/or timeliness.
- Discuss the conduct and progress of the study with the investigator and study center personnel.
- Ask the investigator or designee to clarify or complete data discrepancies.
- Conduct a quality review of the database.
- Verify the quality of the data.

The study center may be audited by government regulatory authorities. The investigator will notify the sponsor in advance of any scheduled regulatory inspection, and within 24 hours of any unscheduled inspection. During an audit, the investigator and study center personnel will cooperate fully and provide access to all study facilities, data and documentation. Any regulatory inspection records will be forwarded to the sponsor promptly.

### **7.2. Direct Data Entry and Computerized Systems**

In this protocol, the term electronic case report form (eCRF) refers to an electronic record of study related- data for an individual patient. An eCRF is required and will be completed for each patient screened in this clinical study. Data will be captured on eCRFs using an electronic data capture (EDC) system, both of which will comply with Title 21 CFR Part 11. The documentation related to validation of the EDC system will be retained by the EDC system vendor, and validation of the study-specific eCRFs will be conducted and maintained by the sponsor.

Data collected on the eCRFs will be stored electronically by the EDC vendor on an externally hosted server. Any other data stored by a vendor (i.e., the results of laboratory testing or ECG data) will be stored electronically on an externally hosted server, and subsequently transferred to the sponsor or designee.

The term source document refers to any original document, data or record containing patient-related information. This may include hospital records, clinical and office charts, laboratory data/information, patient diaries or evaluation checklists, pharmacy dispensing and other records, recorded data from automated instruments, microfiches, photographic negatives, microfilm or magnetic media, x-rays, etc. Data collected during this study must be recorded on the appropriate source documents. The main source document for this study is the patient's medical record. The information collected on the patient's eCRF must match this medical record.

It is the responsibility of the investigator to ensure that eCRFs and source documents are complete and accurate. The investigator will confirm the authenticity of all laboratory and clinical data recorded in the eCRFs by written or electronic signature.

### **7.3. Record Retention**

To permit audits by regulatory authorities or the sponsor, the investigator will retain all study-related documentation. This may include patient records, original signed ICDs, SAE forms, source data, source documents, the study protocol, monitoring visit reports, and sufficient information to identify participating patients. The sponsor will archive data from EDC that pertains to a study center (e.g., patients' final eCRFs) in a durable media format and forward it to the investigator. The records will be retained by the investigator in accordance with the regulatory guidelines.

No study document will be destroyed without prior written agreement from the sponsor, even after the minimum retention period has elapsed.

## 8. PHARMACOKINETIC, PHARMACODYNAMIC, SAFETY, AND EFFICACY DATA ANALYSES

### 8.1. Data Analysis Plans

#### 8.1.1. General Considerations

A detailed statistical analysis plan (SAP) will be developed prior to study completion and database lock, which will describe the endpoints and analyses for the study. Any deviations from the statistical analyses planned in this protocol or the SAP will be described in the clinical study report.

The administration of IMP, dose interruptions, and dose modifications will be listed with the associated reasons. Concomitant medications will be listed by patient with reason for use, dose, route, and date of administration at a minimum, and time of administration if available. Major protocol deviations will be listed by patient and by study center.

Safety analyses will be performed on the Full Analysis Set (all patients who receive at least 1 dose of IMP, whether or not they complete all protocol requirements).

PK analyses will include all patients who receive at least 1 dose of IMP and have PK data that is sufficient and interpretable, as determined by the sponsor.

PD analyses for target engagement will include all patients who receive at least 1 cycle of IMP and from whom samples are collected of sufficient quantity and quality for evaluation. PD analyses for hematological changes will include all patients who receive at least 1 dose of IMP and have PD data that is sufficient and interpretable, as determined by the sponsor.

ORR will be assessed in the Full Analysis Set as well as in all patients evaluable for efficacy (all patients who complete at least 1 cycle of IMP with adequate compliance [as described in [Section 8.5.1](#)], and had a tumor assessment by RECIST v1.1 at baseline and at least once following receipt of IMP). Subsequent analyses of efficacy may be limited to patients evaluable for efficacy.

Analysis of tumor molecular profile will include all patients who complete at least 1 cycle of AK-01, and have blood and pre-treatment tumor samples of sufficient quality and quantity to permit evaluation using next-generation sequencing or other technology. Comparisons of efficacy in patients with specific molecular profiles will include all patients who are evaluable for both efficacy and molecular profile, as described above.

#### 8.1.2. Study Participants

All patients who discontinue the study will be identified, and the extent of their participation in the study will be reported. A reason for their discontinuation will be provided.

#### 8.1.3. Pharmacokinetic and Pharmacodynamic Analyses

PK parameters for AK-01 will be computed by standard non-compartmental methods of analysis. The primary PK parameters are  $AUC_{0-12}$ ,  $AUC_{0-24}$ ,  $C_{max}$  and the time to reach maximum plasma concentration ( $t_{max}$ ). Other PK parameters, such as apparent terminal elimination half-

life ( $t_{1/2}$ ), CL/F, and apparent volume of distribution ( $V_z/F$ ) will also be calculated. PK parameters will be calculated individually and presented with summary statistics.

PD analyses may compare hematological changes between time points, as well as target engagement across time points, and between tissues.

PD results may be presented by patient, in summary tables and graphically.

The relationship between AK-01 PK and PD measures may be evaluated. Modeling may be applied.

#### *8.1.4. Safety Analysis*

All safety data will be listed and tabulated separately for Phase I and II, and analyzed by descriptive statistics.

The results of all scheduled and unscheduled safety assessments will be listed for each patient, with the investigator's assessment of clinical significance. Abnormal results will be listed separately, with clinically significant results flagged.

All AEs will be coded to the appropriate terminology and graded using NCI CTCAE version 4.03. AEs may be summarized by cohort with respect to relatedness to AK-01, outcome, seriousness, severity, action taken, and date and time of onset and resolution. SAEs, DLTs, DLT-equivalent toxicities, and AEs leading to premature withdrawal or death may be summarized. The type of toxicities which are dose-limiting may be explored. Values for ECG parameters and change from baseline may be listed and summarized using descriptive statistics. The relationship between ECG parameters and AK-01 exposure may be explored.

#### *8.1.5. Treatment Compliance*

The investigator or designee will verify that IMP supplies are received intact and in the correct amounts. Records of receipt, storage, loss, and dispensing of IMP to each patient will be kept. The study center will also keep a current and accurate inventory of IMP. Overall accountability of the IMP will be performed by the monitor throughout the study and at the close-out visit.

To confirm treatment compliance, patients must return all AK-01 bottles (empty, partially empty, or full) to the study center as indicated by the schedule in Appendix 1. Study center staff will document the bottles returned and the number of capsules per bottle in source documents.

A patient will be considered compliant with respect to treatment if  $\leq 12\%$  and  $\geq 8\%$  of the assigned dose is taken. Non-compliance in Cycle 1 of Phase I will result in withdrawal of the patient from the study and exclusion of the patient from analysis. Non-compliance in Cycles  $\geq 2$  in Phase I or in Phase II may merit counseling of the patient by the investigator or designee about the importance of study treatment compliance. With continued non-compliance, the investigator may consider withdrawing the patient.

Exploratory analysis of the impact of compliance on selected endpoints may be performed if deemed necessary.

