### 5.2.2. Dose and Regimen

AK-01 will be administered twice daily, every day of a 21-day cycle. Patients will be dosed continuously: there will be no dosing holiday between cycles.

In Phase I, the dose of AK-01 will be between 25-75 mg BID per day (see [Table 3](#)). Patients in the first cohort of Phase I will receive 25 mg BID AK-01. Following a review of safety and other relevant data from this cohort, the SAC will decide on the dose for the subsequent cohort based on [Table 3](#). Following DLT or completion of Cycle 1, dosing for a given patient will be based on individual safety and tolerability.

For Phase II, the sponsor and SAC has established the dose of AK-01 as 25mg BID.

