#### *5.3.2. Evaluable Patients*

Any patient who withdraws from the study before receiving IMP may be replaced.

Any patient in Phase I who is discontinued from the study before completing Cycle 1 or who receives <38 doses of IMP in Cycle 1 will be deemed non-evaluable for DLT assessment at that dose level, unless the patient experiences a DLT. Additional patients may be enrolled to a cohort in Cycle 1 if a patient is withdrawn for reasons other than a DLT (e.g., disease progression, non-compliance, or personal reasons) to ensure that an appropriate number of patients will be evaluated.

Any patient withdrawn for toxicity in Cycle  $\geq 2$  of Phase I will not be replaced.

Any patient withdrawn for toxicity in Phase II prior to completion of Cycle 1 may be replaced.

Any patient who is not evaluable for PK, PD, or biomarkers may be replaced upon consultation with the investigator(s) and the sponsor to ensure collection of sufficient data for interpretation.

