#### **Efficacy Evaluable Analysis Set**

All patients who completed at least 1 cycle of AK-01 with adequate compliance (i.e.  $\geq 80\%$  and  $\leq 120\%$  of the assigned dose was taken) and had a tumor assessment by RECIST v 1.1 at baseline and at least once following receipt of AK-01.

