#### **Relative dose intensity**

Planned dose intensity is the dose by unit of time planned to be given to the patients as per the assigned cohort. Relative dose intensity is defined as Dose intensity/Planned dose intensity.

Cumulative dose, dose intensity and relative dose intensity will be summarized by descriptive statistics by cohort, with respect to an individual duration of treatment exposure as well as by cycle. The relative dose intensity will be summarized as continuous variable as well as by categories (<80%, 80%-120%, >120%).

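### Protocol 8.1.5 sets the compliance window at 8% to 12% of the assigned dose, one tenth of the SAP's 80% to 120%, so a fully dosed patient is non-compliant as written

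*Protocol*

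**What the plan says.** Protocol 8.1.5 (Treatment Compliance) defines the window: "A patient will be considered compliant with respect to treatment if $\leq 12\%$ and $\geq 8\%$ of the assigned dose is taken". It then attaches a consequence: "Non-compliance in Cycle 1 of Phase I will result in withdrawal of the patient from the study and exclusion of the patient from analysis". For later Phase I cycles and for Phase II the consequence is milder: possible counseling and, if non-compliance continues, possible withdrawal.

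Protocol 8.1.1 uses compliance to define the efficacy-evaluable patients, "all patients who complete at least 1 cycle of IMP with adequate compliance", and points to Section 8.5.1 for the definition. The protocol has no such section; the text is in 8.1.5.

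Protocol 5.3.2 has a separate dose-count rule for Phase I: a patient who receives fewer than 38 "doses of IMP in Cycle 1 will be deemed non-evaluable for DLT assessment at that dose level, unless the patient experiences a DLT".

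SAP 8.1 defines the Efficacy Evaluable Analysis Set by completion of at least one cycle "with adequate compliance (i.e. $\geq 80\%$ and $\leq 120\%$ of the assigned dose was taken", plus tumor assessments. SAP 9.7.1 uses the same 80% and 120% cut-offs to categorize relative dose intensity. SAP Section 2 lists one change from the protocol, the type of biopsy in a Phase I exploratory objective, and says nothing about compliance limits.

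**The concern.** The protocol and the SAP give windows that do not overlap, and the difference is not declared. The protocol's window also cannot be met by anyone who takes the drug as prescribed.

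The figure is a decision threshold. In Cycle 1 of Phase I, falling outside it requires withdrawal and exclusion. Followed literally, it would remove fully dosed patients from the data used to set the MTD. In the protocol's own efficacy-evaluable definition, it would shut out every fully dosed patient from one of the two populations in which ORR is assessed.

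**Working it through.** The window is stated without a formula, so there is no calculation of the plan's to reproduce. The check is to convert each window to doses and compare it with the dosing schedule and the 38-dose rule.

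**Inputs**
- Schedule, Protocol 5.2.2: "AK-01 will be administered twice daily, every day of a 21-day cycle". Planned doses per cycle = 21 × 2 = 42.
- Protocol 8.1.5 window: 8% to 12%.
- SAP 8.1 window: 80% to 120%.
- Minimum doses for DLT evaluability without a DLT, Protocol 5.3.2: 38.
- Dose per administration at 25 mg BID: 25 mg, so 42 × 25 = 1050 mg per cycle.

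**Ratio of limits.** 8/80 = 0.10 and 12/120 = 0.10. Each protocol limit is one tenth of its SAP counterpart.

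**Windows in doses and mg**

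| Window | Limits in doses | Whole doses admitted | As % of 42 | mg per cycle at 25 mg BID |
|---|---|---|---|---|
| Protocol 8.1.5 | 0.08 × 42 = 3.36 to 0.12 × 42 = 5.04 | 4 or 5 | 9.5% to 11.9% | 84 to 126 |
| SAP 8.1 | 0.80 × 42 = 33.6 to 1.20 × 42 = 50.4 | 34 to 50 | 81.0% to 119.0% | 840 to 1260 |

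**Full dosing.** 42/42 = 100%, which is above the 12% cap (non-compliant) and inside 80% to 120% (compliant).

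**Against the 38-dose rule.** 38/42 = 90.5%. A patient without a DLT is evaluable with 38 or more doses and compliant under Protocol 8.1.5 with 4 or 5, so no one can satisfy both. This conflict lies within the protocol and does not depend on the SAP. A patient with a DLT is evaluable at any dose count. Under the SAP window, 38 to 42 doses (90.5% to 100%) are all compliant.

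**Choice of period.** Protocol 8.1.5 does not say over what period compliance is measured, so the 42-dose denominator is an assumption. The conclusion does not depend on it, because full dosing is 100% over any period. Over the first 7 days (14 doses) the window is 1.12 to 1.68 and admits no whole number of doses. Over 14 days (28 doses) it is 2.24 to 3.36 and admits only 3.

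**The case against.** **The digits may not be in the source.** Each limit differs from the SAP's by one trailing zero before a percent sign. PDF conversion could cause that as well as a typing error, and the text alone cannot settle which. This stands as a reason to check the source page first. The evidence leans the other way, though: trailing zeros in the same notation survive elsewhere, for example the 20% response threshold in Protocol 3.6, the laboratory limits of 30, 90 and 100 in Protocol 4.1.1, and the 80% and 120% in SAP 8.1. A conversion fault would have had to drop one zero from both numbers in a single sentence.

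**The SAP already works.** Its efficacy-evaluable set uses 80% to 120%. Its DLT set uses the 38-dose rule, and its FAS has no compliance condition. SAP 8.2 says that protocol deviations as such do not exclude patients from analysis sets. No test or estimate in the SAP depends on 8% to 12%. This stands and limits the effect on results. It does not reach the withdrawal instruction, which concerns conduct and appears only in the protocol.

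**No one would apply it literally.** A rule that fails every adherent patient is plainly a misprint. Protocol 1.3 reports 12 patients dosed at up to 75 mg BID, and Protocol 3.1.3 requires at least 3 patients to complete Cycle 1 or have a DLT before escalation. DLTs are mentioned at 50 and 75 mg but not at 25 mg, so patients at 25 mg presumably completed Cycle 1. This is inference, but a reasonable one: the literal rule was probably not enforced.

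**The reach is narrow.** The mandatory action covers only Cycle 1 of Phase I, and the Phase II dose is already chosen. That is correct, although the protocol still describes Phase I as ongoing.

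**Conclusion.** The concern holds. As printed, the compliance window in Protocol 8.1.5 is too low by a factor of ten. It admits 4 or 5 of 42 doses instead of 34 to 50, it fails a patient who takes every dose, and it cannot be reconciled with the protocol's own 38-dose rule for patients without a DLT.

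The practical effect is limited. The intended value is evident, the SAP's analysis sets use workable rules, and Phase II non-compliance triggers nothing mandatory. The protocol's power figures do not depend on the window. There is no indication that any result is biased. The correction should still be made, because the threshold carries a compulsory withdrawal and exclusion in Phase I, and the workable limits appear only in the SAP.

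The conclusion assumes that the printed digits match the source file. The dose counts assume a whole-cycle denominator of 42; the finding that full dosing is non-compliant does not.

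**What to change.** Check the source file. If the digits are confirmed, change Protocol 8.1.5 so that compliance means at least 80% and at most 120% of the assigned dose, matching SAP 8.1 and the cut-offs in SAP 9.7.1. In the same edit, correct the clerical pointer in Protocol 8.1.1 from Section 8.5.1 to Section 8.1.5.

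The 38-dose DLT rule can stay as it is, since 38 to 42 doses lie inside the corrected window. The cost is a one-line protocol clarification plus the pointer. The SAP, the sample size and the analyses do not change.

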#### **Full Analysis Set (FAS)**

All patients who received at least 1 dose of AK-01, whether or not they completed all protocol requirements.

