### 8.2. Protocol Deviations

All protocol deviations will be identified and classified as major/minor before the database lock. No protocol deviations as such will be reasons for exclusion from analysis sets.

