## **9.8. Analyses of Safety**

Unless specified otherwise, all safety analyses will be performed in the FAS. Only safety assessments collected no later than 30 days after the Treatment end date will be summarized in tables. All safety assessments entered in the eCRF

(scheduled and unscheduled) will be listed and the assessments that did not occur within this timeframe will be flagged.

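### Protocol 8.1.5 excludes Phase I Cycle 1 non-compliers from an unnamed analysis, contradicting the Full Analysis Set, SAP 8.2 and the DLT-evaluability rule

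*Protocol*

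**What the plan says.** - Protocol 8.1.5 (Treatment Compliance): "Non-compliance in Cycle 1 of Phase I will result in withdrawal of the patient from the study and exclusion of the patient from analysis". Its definition begins "A patient will be considered compliant with respect to treatment if" and continues with a percentage band of the assigned dose. It does not say how doses withheld for toxicity are counted. In later cycles and in Phase II, non-compliance may lead to counselling and, if it continues, possible withdrawal; exclusion from analysis is not mentioned there.
- Protocol 8.1.1 analyses safety in the Full Analysis Set: "all patients who receive at least 1 dose of IMP, whether or not they complete all protocol requirements".
- SAP 8.1 defines the FAS as "All patients who received at least 1 dose of AK-01, whether or not they completed all protocol requirements". SAP 9.8 adds that, unless specified otherwise, "all safety analyses will be performed in the FAS".
- SAP 8.2: "No protocol deviations as such will be reasons for exclusion from analysis sets".
- Protocol 5.3.2: a Phase I patient who is discontinued before completing Cycle 1, or who "receives <38 doses of IMP in Cycle 1", is not evaluable for DLT at that dose level unless a DLT occurred. The DLT set in SAP 8.1 applies the same rule.
- Among the analysis sets in SAP 8.1, only the Efficacy Evaluable set carries a compliance condition: patients who "completed at least 1 cycle of AK-01 with adequate compliance", given as 80% to 120% of the assigned dose.
- SAP Section 2 lists one change from the protocol, the type of biopsy for a Phase I exploratory objective.

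**The concern.** The 8.1.5 sentence is an unrestricted exclusion of treated patients based on something that happens after dosing starts. The set definitions are written to prevent exactly that. A programmer following 8.1.5 and a programmer following the SAP would produce different Phase I safety tables, and each could cite a governing document. Tolerability and overall safety are the Phase I secondary objective, so these tables carry weight.

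Non-compliance in Cycle 1 also need not be unrelated to tolerability. If doses missed because of side effects count as non-compliance, the exclusion would act on patients who are informative about safety.

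**Working it through.** **Step 1: the rules side by side.**

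| Source | Who is affected | What is lost | DLT exception |
|---|---|---|---|
| Protocol 8.1.5 | Phase I Cycle 1 non-compliers | Analysis, set not named | None |
| Protocol 8.1.1; SAP 8.1 (FAS); SAP 9.8 | Nobody who took at least 1 dose | Nothing | Not needed |
| SAP 8.2 | Nobody, on the ground of a deviation as such | Nothing | Not needed |
| Protocol 5.3.2; SAP 8.1 (DLT set) | Fewer than 38 doses, or off study before the end of Cycle 1 | DLT evaluability only | Yes |

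The first row cannot hold together with the second and third. It agrees with the fourth only if the unnamed analysis is taken to be the DLT analysis and the DLT exception is read in.

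**Step 2: are 8.1.5 and 5.3.2 the same rule?** Protocol 5.2.2 gives twice-daily dosing for 21 days, so Cycle 1 has 2 × 21 = 42 planned doses.
- DLT threshold: 38/42 = 90.5%.
- SAP compliance floor: 0.80 × 42 = 33.6, so at least 34 doses. 34/42 = 81.0% passes; 33/42 = 78.6% fails.
- A patient with 34 to 37 doses and no DLT is therefore compliant but not DLT-evaluable.

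The cut-offs differ. The 80% floor is borrowed from the SAP because the protocol band, as it reads in the text available here, is 8% to 12%. On 42 doses that is 3.36 to 5.04, or 4 to 5 doses, and a patient taking all 42 would fail. This may be a PDF reading error for 80% and 120%, so nothing here rests on it.

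**Step 3: what the exclusion adds to Section 5.3.2.** Using the SAP floor, an under-dosed non-complier has at most 33 doses. Without a DLT, that patient is already outside the DLT set, because 33 is below 38. The exclusion changes nothing there. For under-dosed patients its added effect is on analyses that otherwise include all treated patients, chiefly safety and the Phase I ORR in the FAS (SAP 9.6.2). It would also conflict with two planned outputs:
- SAP 9.7.1 tabulates relative dose intensity by cycle with a category below 80%, which would lose its under-dosed Phase I Cycle 1 patients.
- Protocol 8.1.5 itself allows an exploratory look at the effect of compliance on endpoints, which needs the non-compliers.

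**Step 4: do toxicity holds count as non-compliance?** No section says. Protocol 3.1.1 requires interruption after a DLT, 3.3.2 permits holds of up to 21 days, and 5.3.2 lists non-compliance among reasons other than a DLT. These point towards no. On the other side, SAP 9.7.1 includes interruptions in the duration used for dose intensity and compares the result with the dose planned for the assigned cohort. If compliance were computed that way, 42 − 33 = 9 missed doses, about 4.5 days, would make a patient non-compliant.

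**Step 5: size.** Protocol 1.3 reports 12 Phase I patients dosed; the synopsis allows up to 30. One excluded patient is 1/12 = 8.3% or 1/30 = 3.3% of the Phase I safety population, and 1/3 of an initial dose cohort of three. The number of actual non-compliers is not given.

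**The case against.** The strongest reply is that the operative definitions already agree. Safety is analysed in the FAS, DLTs in the DLT set, and no SAP set implements the 8.1.5 exclusion. The sentence is confined to Cycle 1 of Phase I, which is the DLT window, so it may be loose wording for DLT evaluability. The Phase II dose is already chosen, and the Phase II ORR test is untouched.

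Most of this stands as a limit on the consequences. It does not remove the contradiction: 8.1.5 does not say that it concerns DLT evaluability, its threshold is not the 38-dose threshold, and SAP Section 2 does not set it aside. Protocol 8.1.1 requires deviations from the planned analyses to be described in the study report, so following the SAP would itself need explaining.

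A reader might draw two stronger conclusions that the documents do not support:
- **That patients who stopped for toxicity will be removed.** This needs withheld doses to count against the assigned dose, which no section says and which Protocol 3.1.1, 3.3.2 and 5.3.2 tend against. Removal is possible, not established.
- **That a DLT could vanish from a cohort of three, turning 1/3 into 0/2 and distorting escalation.** Protocol 5.3.2 and the SAP DLT set expressly keep any patient with a DLT. Protocol 3.1.3 requires at least 3 patients to complete Cycle 1 or have a DLT before an escalation decision, so 0/2 could not support one.

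**Conclusion.** The contradiction is established from the text alone and needs no assumption about how compliance is computed. As written, the 8.1.5 clause would drop treated patients from the Phase I safety analysis, against the protocol's own Full Analysis Set and three SAP provisions (the FAS, the safety population and the deviation rule). It also conflicts with the DLT-evaluability rule by omitting the DLT exception.

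The link to toxicity is conditional: it holds only if withheld doses are counted against the assigned dose. For patients with a DLT to leave the DLT set, 8.1.5 would also have to override the explicit exception.

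The effect is on Phase I reporting, at 3.3% to 8.3% of the safety population per excluded patient (30 and 12 patients respectively). It should be corrected because the remedy is nearly free and the clause, if followed, would produce the wrong safety population.

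**What to change.** In Protocol 8.1.5, do one of the following:
- delete the closing clause that removes the patient from analysis; or
- limit it to DLT evaluability under Section 5.3.2, so that the patient is not evaluable for DLT unless a DLT occurred.

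With either option, add that all treated patients stay in the Full Analysis Set and that protocol-directed holds for toxicity are not non-compliance for analysis purposes. Define the assigned dose, and state which threshold (38 doses, or 80% to 120%) governs which set. Check the protocol's printed compliance band against the source file.

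If the protocol is not amended again, record in SAP Section 2 that the exclusion is not applied, and why.

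Whether a non-compliant patient is withdrawn from the study is a clinical rule on which no view is taken here. Protocol Sections 3.3.2, 5.3.2 and 8.1.5 should be reconciled on it.

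The cost is a few sentences. No sample size, power, alpha or data collection changes.
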